## METHODS

### Design

The Isotonic Solutions and Major Adverse Renal Events Trial (SMART) is a prospective, unblinded, pragmatic, cluster-level-allocation, cluster-level-crossover trial being conducted between June 1, 2015 and April 30, 2017 in five ICUs at Vanderbilt University Medical Center in Nashville, TN. SMART compares saline (0.9% sodium chloride) to balanced crystalloids (Lactated ringers and Plasma-Lyte A®) with regard to the primary outcome of Major Adverse Kidney Events within 30 days (MAKE30) – the composite of in-hospital death, receipt of new RRT, or persistent renal dysfunction (discharge creatinine  $\geq$  200% of baseline creatinine). Consistent with the concept of a pragmatic clinical trial[18,19], eligibility criteria are broad, the sample size is large, and study procedures are embedded into routine care and executed by clinical personnel. The trial was approved by the Vanderbilt University Medical Center Institutional Review Board (IRB) with waiver of informed consent (IRB#141349). The trial was registered with ClinicalTrials.gov prior to initiation of patient enrollment (NCT02444988; NCT02547779). An independent Data and Safety Monitoring Board (DSMB) is monitoring the progress and safety of the trial. The trial is investigator-initiated with funding provided by the Vanderbilt Institute for Clinical and Translational Research through a Clinical and Translational Science Award (CTSA) from the National Center for Advancing Translational Sciences (UL1 TR000445).

### Study Sites and Period

SMART is being conducted in five academic ICUs at Vanderbilt University Medical Center: a 34-bed medical ICU, a 22-bed neurological and neurosurgical ICU, a 27-bed cardiovascular ICU, a 31-bed trauma ICU, and a 22-bed surgical ICU. Participating ICUs began enrollment sequentially over the first year of the study (Figure 1). Each ICU will enroll patients for at least 12 months and will enroll for an equal number of saline and balanced crystalloid months.

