### **5.0 Study Description**

This is a single-center, cluster-randomized, multiple-crossover trial comparing balanced crystalloids to saline with regard to death, new RRT, or persistent renal dysfunction. The participating ICUs will be randomized to utilization of 0.9% sodium chloride or balanced crystalloids (lactated Ringers or Plasma-Lyte A®). Every patient admitted to an ICU at Vanderbilt Medical Center during the study period who meets no exclusion criteria will be enrolled and will receive the assigned study fluid if isotonic crystalloid is ordered by the treating provider and none of the pre-specified contraindications are present. All other decisions regarding fluid administration

Principal Investigators: [name], [name]

Version Date: 6/15/17

Study Title: Isotonic Solutions and Major Adverse Renal Events Trial (SMART)

Institution/Hospital: Vanderbilt University Medical Center

including indication, timing, rate, volume, and endpoint will remain at the discretion of the treating provider. The study will not impact the use of oral fluids or other IV fluids. Every month each ICU will undergo a cross-over in assigned fluid group such that each ICU will experience each fluid group assignment for equal time periods during the study.

For logistical purposes, the study will be registered as two, independent, parallel, randomized, multiple-crossover trials – one for patients enrolled from the medical ICU (SMART-MED) and one for patients enrolled from the other ICUs (SMART-SURG). Success of the pilot study (SALT) in the MICU of establishing the infrastructure needed to deliver the study intervention will allow enrollment in SMART-MED to begin immediately in the MICU. The initiation of enrollment in the other ICUs (SMART-SURG) will be dependent on successfully transferring the infrastructure for delivery of the assigned intervention to these ICUs and is anticipated to be delayed 6 months from the start of the SMART-MED trial. SMART-MED and SMART-SURG will have an identical design, intervention, and data collection to allow for analysis of all patients concurrently in accordance with a single, pre-specified data-analysis plan.

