#### **Final Sample Size Justification**

*(Protocol Amendment 5/10/16; Published with Statistical Analysis Plan 3/16/17)*

As a cluster-randomized, multiple-crossover trial, SMART will enroll for a fixed duration to account for seasonal effects and ensure an equal number of study periods in which each study unit is assigned to each study arm. The final planned study duration is 82 unit-months over a calendar period of two years. The total number of patients enrolled will depend on the rate of admissions to study ICUs during the fixed time period of the trial.

Principal Investigators: [name], [name]

Version Date: 6/15/17

Study Title: Isotonic Solutions and Major Adverse Renal Events Trial (SMART)

Institution/Hospital: Vanderbilt University Medical Center

Based on data from the study ICUs in the year prior to the trial, we anticipated that the final planned study duration of 82 unit-months would result in enrollment of around 14,000 patients with an overall rate of MAKE30 around 15%. Enrollment of 14,000 patients would provide 90% power at an alpha level of 0.05 to detect an absolute difference between the saline and balanced crystalloid groups in MAKE30 of 1.9%, a relative risk reduction of 12%. This relative risk reduction is similar to the relative risk reduction reported in prior research comparing balanced crystalloid to saline among critically ill adults.

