### **Final Anticipated Sample Size**

*(Protocol Amendment 3/29/17)*

As a cluster-randomized, multiple-crossover trial, SMART will enroll for a fixed duration, 82 unit-months over a calendar period of two years, and the total number of patients enrolled will depend on the rates of admissions to study ICUs during the fixed time period of the trial. The number of patients admitted to each of the participating ICUs has increased over the duration of the trial and we now anticipate at least 15,000 and no more than 16,500 patients will be enrolled during the planned study period.

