### **Final Plan for Interim Analyses**

*(Protocol Amendment 5/10/16, Published with Statistical Analysis Plan 3/16/17)*

With the final study duration of 82 unit-months over two calendar years, the DSMB will conduct two interim analyses. The first will occur 6 months after study initiation. The second will occur halfway between the first interim analysis and the end of the trial. Both interim analyses will use the same stopping criteria. The stopping boundary for efficacy will be met if (1) the unadjusted difference in the incidence of the primary outcome (MAKE30) between study groups is greater than or equal to 2.6% with a P value less than 0.001 AND (2) the P value is less than 0.001 for the difference between study groups in the incidence of either in-hospital mortality or receipt of new RRT. As even small differences between groups would be clinically meaningful, and given the importance of determining with as much certainty as possible whether balanced crystalloids are superior to saline, a futility stopping boundary will not be employed. Use of the conservative Haybittle-Peto boundary ( $P < 0.001$ ) will allow the final analysis to be performed using an unchanged level of significance ( $P = 0.05$ ).

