## Abstract

**Background:** Saline, the intravenous fluid most commonly administered to critically ill adults, contains a high chloride content, which may be associated with acute kidney injury and death. Whether using balanced crystalloids rather than saline decreases the risk of acute kidney injury and death among critically ill adults remains unknown.

**Methods:** The Isotonic Solutions and Major Adverse Renal Events Trial (SMART) is a pragmatic, cluster-level allocation, cluster-level crossover trial being conducted between 1 June 2015 and 30 April 2017 in five intensive care units at Vanderbilt University Medical Center in Nashville, TN, USA. SMART compares saline (0.9% sodium chloride) with balanced crystalloids (clinician's choice of lactated Ringer's solution or Plasma-Lyte A®). Each intensive care unit is assigned to provide either saline or balanced crystalloids each month, with the assigned crystalloid alternating monthly over the course of the trial. All adults admitted to participating intensive care units during the study period are enrolled and followed until hospital discharge or 30 days after enrollment. The anticipated enrollment is approximately 14,000 patients. The primary outcome is Major Adverse Kidney Events within 30 days—the composite of in-hospital death, receipt of new renal replacement therapy, or persistent renal dysfunction (discharge creatinine  $\geq 200\%$  of baseline creatinine). Secondary clinical outcomes include in-hospital mortality, intensive care unit-free days, ventilator-free days, vasopressor-free days, and renal replacement therapy-free days. Secondary renal outcomes include new renal replacement therapy receipt, persistent renal dysfunction, and incidence of stage 2 or higher acute kidney injury.

**Discussion:** This ongoing pragmatic trial will provide the largest and most comprehensive comparison to date of clinical outcomes with saline versus balanced crystalloids among critically ill adults.

**Trial registration:** For logistical reasons, SMART was prospectively registered separately for the medical ICU (SMART-MED; ClinicalTrials.gov identifier: NCT02444988; registered on 11 May 2015; date of first patient enrollment: 1 June 2015) and the nonmedical ICUs (SMART-SURG; ClinicalTrials.gov identifier: NCT02547779; registered on 9 September 2015; date of first patient enrollment: 1 October 2015).

**Keywords:** Intravenous fluids, Crystalloid, Saline, Renal failure, Pragmatic trial

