## Study sites and period

SMART is being conducted in five academic ICUs at Vanderbilt University Medical Center: a 34-bed medical ICU, a 22-bed neurological and neurosurgical ICU, a 27-bed cardiovascular ICU, a 31-bed trauma ICU, and a 22-bed surgical ICU. Participating ICUs began enrollment sequentially over the first year of the study (Fig. 2). Each ICU will enroll patients for at least 12 months and will enroll participants for an equal number of saline and balanced crystalloid months.

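### Equal saline and balanced months in every ICU cannot be squared with the stated dates and monthly alternation, and the 82 unit-months do not match the printed schedule

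*Combined protocol and SAP*

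**What the plan says.** **Equal months.** The SAP, under Study Sites and Period, states that each ICU "will enroll for an equal number of saline and balanced crystalloid months". The published protocol repeats this ("will enroll participants for an equal number of saline and balanced crystalloid months"). The final protocol (version 6/15/17), section 5.0, says that "each ICU will experience each fluid group assignment for equal time periods during the study". Its section 12.0, Final Sample Size Justification, explains that enrollment runs for a fixed duration partly to "ensure an equal number of study periods in which each study unit is assigned to each study arm".

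**Dates.** The SAP Design section describes the trial as "being conducted between June 1, 2015 and April 30, 2017 in five ICUs". The published abstract gives 1 June 2015 as the first enrollment in the medical ICU. For the non-medical registration it gives "registered on 9 September 2015; date of first patient enrollment: 1 October 2015". The same abstract says the assigned fluid alternates monthly.

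**Total.** The duration is put at "82 unit-months over a calendar period of two years" in the Final Anticipated Sample Size section, and again in the interim plan ("With the final study duration of 82 unit-months over two calendar years"), the Final Sample Size Justification and SAP Appendices 3 and 4. The SAP also sets a minimum of 12 months per ICU and, in its Discussion, at least eleven crossovers per unit.

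**Schedule.** The month-by-month assignment is printed twice: SAP Figure 1 and Fig. 2 of the published protocol.

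**The concern.** Strict monthly alternation gives equal months only when an ICU contributes an even number of them. If the dates imply an odd number, the plan claims a design property that its dated schedule does not have, and the protocol uses that property to justify the fixed duration. A reader also cannot tell how many unit-months were planned.

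SAP Appendix 3 says MAKE30 varies between ICUs. If the ICUs are not equally represented in the two arms, the crude proportions that the SAP will print beside the adjusted odds ratio can differ slightly through ICU mix alone. An analysis that does not adjust for ICU is open to the same effect.

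**Working it through.** **1. Months per ICU.**
- Medical: June 2015 to April 2017 = 7 + 12 + 4 = 23 months. Both printings start and end with saline: 12 saline, 11 balanced. This needs only the stated dates and alternation. The SAP's account of emergency department coordination with this unit also runs to 30 April 2017.
- Neuro: October 2015 to April 2017 = 19 months: 9 saline, 10 balanced, the same in both printings.
- Cardiac: December 2015 to April 2017 = 17 months: 8 saline, 9 balanced, the same in both printings.
- Trauma and surgical: the printings disagree (14 v 15 months and 11 v 12 months). The rows may have been damaged when the text was extracted, so they are not used as evidence.

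**2. The stated 82.**
- An all-even set reproduces it: 22 + 18 + 16 + 14 + 12 = 82.
- Prose dates plus the 12-month minimum: 23 + 19 + 12 + 12 + 12 = 78. This is a lower bound and does not contradict 82.
- Adding the cardiac row: 23 + 19 + 17 + 12 + 12 = 83, which exceeds 82. Equivalently, 82 − 59 = 23 months would remain for two units that each need at least 12.
- Summed as printed, the two schedules give 84 and 86.

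**3. Size of a shift in the crude proportions.** Shift = Σ over ICUs of (share of saline arm − share of balanced arm) × assumed MAKE30 rate. The documents give no ICU-specific rates, so these are assumptions. Annual volumes come from the May 2015 protocol version (section 12.0, Figure 12B): medical 2,300, surgical 2,126, cardiac 1,892, trauma 1,693, neuro 1,212.

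Worked example, assuming trauma from March 2016 (7/7) and surgical from May 2016 (6/6), both on the medical ICU's sequence as the SAP's randomization section requires:
- Saline weights (volume × months): 27,600 + 10,908 + 15,136 + 11,851 + 12,756 = 78,251 (medical, neuro, cardiac, trauma, surgical).
- Balanced weights: 25,300 + 12,120 + 17,028 + 11,851 + 12,756 = 79,055.

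| ICUs | Saline share | Balanced share | Difference (points) |
|---|---|---|---|
| Medical | 35.27% | 32.00% | +3.27 |
| Neuro + cardiac | 33.28% | 36.87% | −3.59 |
| Trauma + surgical | 31.45% | 31.13% | +0.32 |

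- Rates 20% medical, 10% neuro/cardiac, 15% trauma/surgical: 3.27×0.20 − 3.59×0.10 + 0.32×0.15 = +0.34 points. Swapping the 20% and 10% gives −0.34.
- Rates 16%, 14%, 15%: 3.27×0.16 − 3.59×0.14 + 0.32×0.15 = +0.07 points.

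Letting trauma and surgical each start in any month from January to May 2016 (25 pairs), and using either 2,300 or 3,000 medical admissions a year (the latter from section 7.2 of the same 2015 version), the first assumption gives 0.32 to 0.36 points and the second 0.06 to 0.07. Total unit-months over these pairs run from 83 to 91.

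**4. Efficiency and power.** A 12:11 split keeps 4×12×11/23² = 528/529 = 99.8% of the efficiency of an equal split. The stated power reproduces: √[(0.15×0.85 + 0.131×0.869)/7,000] = 0.00587; 0.019/0.00587 − 1.96 = 1.28, or 90%. More unit-months than 82 would not lower it.

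**5. Main secondary model.** The SAP's Main Secondary Analysis lists study group, total crystalloid volume and their product as the independent variables. ICU is not listed. The primary model has ICU as a random effect, and the SAP reports an intra-cluster correlation of 0.142 for MAKE30 in pre-trial data.

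**The case against.** **The 82 may not be an error.** It agrees with the equal-months statement. Suppose trauma began in March 2016 and surgical in May 2016, the only printed start months that fit the shared sequence. The schedule then totals 23 + 19 + 17 + 14 + 12 = 85, three more than 82, and three ICUs have one unpaired month, April 2017. So 82 could be a count of paired months. That is an inference, since the documents do not say it, but it stands as a reason not to call 82 wrong.

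**The 83 depends on one extracted table row.** This is true. With cardiac one month shorter the bound would be 82. Against that, the cardiac row is the same in both printings and has the sequence opposite to the medical ICU, as the SAP requires. Some doubt remains. Likewise, neuro's end month comes from the schedule, because the prose gives an end date for the trial and not for each unit.

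**The consequence is slight.** This also stands. The primary model includes ICU, Table 1 will show ICU by arm, and the larger crude shift needs a two-to-one contrast in assumed rates.

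**The logistic model is a separate matter.** Correct: it does not follow from the month count and is put forward separately.

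A reader might infer that the unadjusted interim comparison was compromised. The documents do not support that. On the printed rows, medical and neuro are balanced at the first cut (3/3, 1/1), and medical, neuro and cardiac at the second (7/7, 5/5, 4/4). Trauma or surgical could have had one extra balanced month by 31 July 2016, depending on an uncertain start month. The SAP reports both interim analyses completed, with a recommendation to continue.

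**Conclusion.** The inconsistency is real and minor. On the stated dates with monthly alternation, the medical ICU cannot have equal months: it has 12 saline and 11 balanced. Neuro (9/10) and cardiac (8/9) are unequal too, on schedule rows that agree in both printings. The 82 unit-months conflicts with the April 2017 end date taken together with the printed schedule, where the minimum is 83, but not with the prose dates alone. Which of the wording, end date, schedule or total is wrong cannot be settled from the documents.

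It would be tempting to conclude that the primary result is biased by unequal allocation. The documents do not support this: the primary mixed model includes ICU, and the loss of efficiency is negligible. The crude proportions may shift by about 0.07 points at assumed rates of 16/14/15%, or 0.3 to 0.4 points at 20/10/15%, with either sign. Those figures rest on assumed ICU rates and on volumes from the 2015 protocol version.

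The main secondary logistic model, as described, omits the unit of allocation. The R code is in an additional file that was not available, so it may already include ICU. No effect on that model was quantified.

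**What to change.** - Reconcile the equal-months wording (final protocol sections 5.0 and 12.0; SAP and published protocol, study sites and period), the end date, the 82 unit-months and the two schedule printings. If the dates stand, say that months are equal to within one per ICU where that is so.
- Add a small table of actual saline and balanced months for each ICU, with start and end months.
- Separately, and whatever the month count, include ICU in the main secondary logistic model, as the primary model does, or confirm that the R code already does so.

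The cost is a few sentences, one small table and one model term. ICU-standardised MAKE30 proportions, or a sensitivity analysis without April 2017 in the medical, neuro and cardiac ICUs, are optional and not needed to resolve the point.

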## Population

All adults (age  $\geq 18$  years) admitted to a participating ICU at Vanderbilt University Medical Center during the study period are enrolled at the time of ICU admission. Enrolled patients who are discharged from the hospital are eligible again if they are admitted to a participating ICU again during the study period.

## Consent

Saline, Lactated ringers, and Plasma-Lyte A® are all intravenous crystalloids currently used in the routine care of patients admitted to the ICUs at Vanderbilt University Medical Center. Currently, no high quality data suggest that choice of crystalloid affects clinical outcomes among critically ill adults. During the SMART trial, each time a study crystalloid is ordered, the study confirms that the treating clinician does not feel that any study crystalloid is required for the safe treatment of that specific patient at that specific point in time (see *Study Interventions*). The trial is felt to pose minimal risk because (1) exposure to the study crystalloids occurs only for patients whose treating clinician has already decided to administer an IV crystalloid, (2) all of the crystalloid solutions examined are already used in routine practice in the study environment, (3) no definitive prior data suggest clinical outcomes are better with one crystalloid relative to the others, and (4) the study confirms with every crystalloid order that the treating clinician does not feel any one crystalloid type is required for safe treatment of the patient. Given the minimal risk, the focus of the study on crystalloid use at an ICU level, and the impracticability of consenting each patient admitted to each ICU prior to the first administration of crystalloid, a waiver of informed consent was granted by the Vanderbilt institutional review board (IRB#141349).

## Randomization and Allocation

Each month of the study, each ICU is assigned to either saline or balanced crystalloids. So that each ICU would experience an equal number of months assigned to saline and balanced crystalloids while minimizing monthly imbalances in the hospital's overall use of each crystalloid, we generated two sequences of study group assignment ([1] saline during odd-numbered months and balanced crystalloid during

even-numbered months; [2] balanced crystalloid during odd-numbered months and saline during even-numbered months) and planned for three ICUs to be assigned to one sequence and the remaining two ICUs to the opposite sequence. To facilitate the early administration of the assigned crystalloid in the ED and operating room prior to the patient's physical arrival in the ICU, a single computer-generated, simple randomization was performed in which the three ICUs that admit the majority of patients from the ED (medical ICU, trauma ICU, and surgical ICU) were randomized 'en bloc' to one sequence of crystalloid group assignments and the two ICUs that admit the majority of patients from the operating room (neurological ICU and cardiac ICU) were randomized 'en bloc' to the opposite sequence of crystalloid group assignments (Figures 1-2).

### Concealment and Blinding

As available laboratory values overtly reflect the crystalloid being used and prior studies have shown high levels of provider awareness of crystalloid assignment despite attempts at blinding[13], patients, clinicians, and investigators are not blinded to crystalloid assignment. All study data, including the objective primary outcome, will be electronically extracted from the medical record in an automated manner unaffected by study group assignment.

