## **8.4 Data Collection**

### **8.4.1 Data at Enrollment**

1. Study Enrollment Data:
  - a. Encounter Number ("Study ID")
  - b. Medical Record Number
  - c. Date and Time of ICU Admission ("Time Zero")
  - d. Study ICU at enrollment (Medical/Cardiac/Neuro/Trauma/Surgical)

Principal Investigators: [name], [name]

Version Date: 6/15/17

Study Title: Isotonic Solutions and Major Adverse Renal Events Trial (SMART)

Institution/Hospital: Vanderbilt University Medical Center

2. Demographic Data:

- a. Age (years)
- b. Gender (male/female)
- c. Race (White/Black/Asian/Alaskan/PacificIsland/Other)
- d. Ethnicity (Hispanic, Non-hispanic)
- e. Height (cm)
- f. Weight (kg)
- g. Date and time of Hospital Admission
- h. Source of admission to ICU (ED/OR/outside hospital transfer/hospital ward/outpatient/another ICU within the hospital)
- i. Admitting service
- j. ICD-9 and ICD-10 diagnoses

3. Comorbidities:

- a. Exlihauser comorbidities
- b. CKD stage III or greater by CKD-EPI criteria
- c. Prior receipt of renal replacement therapy
- d. Predicted risk of in-hospital mortality by University HealthSystem Consortium expected in-hospital mortality

4. Invasive Support:

The following information will be recorded during the 12 hours prior to and 24 hours following ICU admission (“Time Zero”). If more than one value is available for this 36-hour period, the value closest to the time of ICU admission (“Time Zero”) will be recorded.

- a. Receipt of Mechanical Ventilation (Y/N)
- b. Receipt of vasopressors (Y/N) (norepinephrine, epinephrine, dopamine, phenylephrine, or vasopressin)

5. Renal function

- a. All serum creatinine values from the clinical laboratory system between 12 months prior to hospitalization and 30 days after ICU admission
- b. Stage II or greater acute kidney injury by KDIGO creatinine criteria

6. Serum laboratory values

- a. All serum values for sodium, potassium, chloride, bicarbonate, and blood urea nitrogen between 12 months prior to hospitalization and 30 days after ICU admission

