### Power Calculation

Based on data from the study ICUs in the year prior to the trial, we anticipate the planned study duration (Figure 1) will result in enrollment of around 14,000 patients with an overall rate of MAKE30 around 15%. Enrollment of 14,000 patients will provide 90% power at an alpha level of 0.05 to detect an absolute difference between the saline and balanced crystalloid groups in MAKE30 of 1.9%, a relative risk reduction of 12%, which is comparable to the 12% relative risk reduction for in-hospital mortality reported in a recent pilot trial[13] (additional details in the Appendix 3).

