**Table E4. Serum laboratory values.**

Laboratory value	Saline (n = )	Balanced (n = )	P value
Serum sodium, mmol/L			
Highest between enrollment and day 30, median [IQR]	--	--	--
Lowest between enrollment and day 30, median [IQR]	--	--	--
>145 between enrollment and day 30, No. (%)	--	--	--
< 135 between enrollment and day 30, No. (%)	--	--	--
Serum potassium, mmol/L			
Highest between enrollment and day 30, median [IQR]	--	--	--
Lowest between enrollment and day 30, median [IQR]	--	--	--
> 5.0 between enrollment and day 30, No. (%)	--	--	--
< 3.0 between enrollment and day 30, No. (%)	--	--	--
Serum chloride, mmol/L			
Highest between enrollment and day 30, median [IQR]	--	--	--
Lowest between enrollment and day 30, median [IQR]	--	--	--
> 110 between enrollment and day 30, No. (%)	--	--	--
< 90 between enrollment and day 30, No. (%)	--	--	--
Serum bicarbonate, mmol/L			
Highest between enrollment and day 30, median [IQR]	--	--	--
Lowest between enrollment and day 30, median [IQR]	--	--	--
> 30 between enrollment and day 30, No. (%)	--	--	--
< 20 between enrollment and day 30, No. (%)	--	--	--

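### Table E4's any-value and highest/lowest rows, and in the same form highest creatinine and stage II AKI, depend on how often unblinded clinicians order tests, which the SAP neither reports nor standardises by arm

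*Combined protocol and SAP*

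**What the plan says.** SAP, Concealment and Blinding: "patients, clinicians, and investigators are not blinded to crystalloid assignment", because laboratory values reveal the fluid in use. The next sentence describes the data as "electronically extracted from the medical record in an automated manner unaffected by study group assignment". SAP, Data Collection: values come from routine care, and no sampling schedule is set.

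SAP Table E4 gives four rows for each of sodium, potassium, chloride and bicarbonate: the highest value, the lowest value, and the number of patients with any value above or below a cut-off. The table has a P value column. The potassium row, for instance, counts patients with a value "> 5.0 between enrollment and day 30, No". Under Secondary Outcomes and Appendix 2, highest creatinine, change to highest creatinine and stage II AKI also use any value in the window.

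The text of Secondary Outcomes defines the biochemical outcomes as serum values from enrollment to day 30, and Statistical Analysis Principles assigns generalized estimating equations to repeated measures. The 2017 protocol, 8.4.1 item 6, collects "All serum values for sodium, potassium, chloride, bicarbonate, and blood urea nitrogen between 12 months prior to hospitalization and 30 days after ICU admission"; item 5 does the same for creatinine.

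The SAP Discussion accepts that unblinded clinicians may change fluid use, and for that reason commits to reporting fluids and blood products. It makes no such commitment for test ordering.

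**The concern.** A maximum, a minimum or an any-value count is taken over however many samples exist. The more often a patient is tested, the more likely some value crosses the cut-off. Here testing is ordered by people who know the assignment. There is also an arm-specific potassium consideration in view: the order advisor lists hyperkalemia as a relative contraindication to balanced fluid only (SAP, Study Interventions). Automated extraction prevents observer bias but leaves this route open.

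The 2017 protocol, section 10.0, has potassium, sodium, chloride and acid-base disturbances recorded as study outcomes, and does not report them individually to the IRB unless they are thought related to the intervention. Table E4 is therefore a main between-group record of these events. Without draw counts, a reader cannot tell a fluid effect from a testing difference. A real effect could also be hidden in the arm tested less.

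**Working it through.** **1. The plan's own figure.** SAP, Power Calculation, expects "14,000 patients with an overall rate of MAKE30 around 15" percent, with 90% power at alpha 0.05 for a difference of 1.9 points. Take 7,000 per arm and 15.0% against 13.1%. The null SE is sqrt(2 × 0.1405 × 0.8595 / 7,000) = 0.00587, so the critical difference is 1.96 × 0.00587 = 0.01151. Power = Φ((0.0190 − 0.01151) / 0.00587) = 89.9%. The figure reproduces; it serves only to show that the same test formula is used below.

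**2. Sample size.** The 2017 protocol, Final Anticipated Sample Size, expects that "at least 15,000 and no more than 16,500 patients will be enrolled". The lower bound split equally gives 7,500 per arm. At 16% incidence, the difference that reaches P<0.05 is 1.96 × sqrt(2 × 0.16 × 0.84 / 7,500) = 1.17 points.

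**3. Model with no fluid effect.** Every variance and draw count is assumed, because the documents give none. Patient level b ~ N(μ, sb); each draw ~ N(b, sw); number of draws n = 1 + Poisson(m − 1). With p(b) the chance that one draw crosses the cut-off:

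incidence = E[1 − (1 − p)^n] = 1 − E_b[(1 − p(b)) × exp(−(m − 1) p(b))].

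Inputs (μ, sb, sw, cut-off):
- potassium 4.1, 0.35, 0.35, >5.0
- chloride 104, 4.5, 2.5, >110
- bicarbonate 24, 3, 2, <20
- sodium 139, 3, 2.2, >145

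Mean draws m = 5 or 8. The implied within-patient correlations (ICC = sb² / (sb² + sw²)) are 0.50, 0.76, 0.69 and 0.65.

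**4. Worked example, potassium, m = 8.** Incidence is 16.0%. With 10% more draws it is 16.9% (0.95 points): Φ((0.0095 − 0.01186) / 0.00605) = 35%. With 20% more it is 17.8% (1.84 points): Φ((0.0184 − 0.01199) / 0.00611) = 85%.

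**5. Range of P<0.05 with no fluid effect, 7,500 per arm.**

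| Extra draws in one arm | Four analytes, m = 5 or 8 | Shift (points) | Potassium, ICC 0.9 |
|---|---|---|---|
| 5% | 10-13% | 0.4-0.6 | 6% |
| 10% | 24-35% | 0.8-1.2 | 8-9% |
| 20% | 66-85% | 1.5-2.3 | 18-19% |

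The last column keeps potassium's total SD, sqrt(0.35² + 0.35²) = 0.495, and sets sb = 0.470 and sw = 0.157.

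**6. Wider assumptions.** With 7,000 per arm, ICC 0.5 to 0.9, about 4 to 8 draws, incidence 10% to 40%, and a variant with serially correlated values, the threshold rows reject in 5-17%, 7-46% and 14-93% for nominal increases of 5%, 10% and 20%. (In the serial variant these were about 4%, 8% and 17% more draws.) The highest-value comparison by Mann-Whitney, in the exchangeable model only, rejects in 6-19%, 12-63% and 30-99%.

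**7. Draws that react to the value.** If extra draws come only after a value has already crossed the cut-off, the threshold row does not move (25% stays at 25%, rejection 5%). The mean of all values then shifts by 0.03 to 0.14 SD.

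**8. What a once-daily version does.** Extra draws on days already sampled no longer count. Extra sampled days still do, because the step 3 formula then applies with days in place of draws. In one simulated setting, again with assumed inputs, false rejection fell from 79% to 5% when the extra draws were within days, but only from 51% to 39% when they fell on extra days.

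**The case against.** Much of the case on the other side stands.

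- A reader might infer that the SAP's statement on automated data is false. It is not. Its words describe extraction, and the sentence before it says plainly that clinicians are unblinded.
- A reader might infer that the laboratory results are biased. No passage shows or quantifies unequal sampling. The advisor asks about hyperkalemia already present when fluid is ordered; it does not prompt a test. Step 7 shows that repeats after an abnormal value leave the threshold rows alone.
- A reader might infer that all laboratory outcomes are extremes. The text defines them as serial values analysed by generalized estimating equations, and Table E4 is a supplemental display. Step 7 shows, though, that the serial comparison is not automatically immune.
- The size depends heavily on the assumed correlation. At ICC 0.9, 20% more draws gives P<0.05 for potassium in under a fifth of trials.
- Draws unrelated to the value should raise high and low rows together in one arm, unlike a one-directional fluid effect. That is a useful clue, but draw counts are needed to confirm it.
- Secondary comparisons are labelled hypothesis-generating. That limits the claim made from these rows; it does not make the counts comparable.
- The 2015 protocol, 8.4.2, recorded highest and lowest values as well as the value closest to 0800, so it does not favour once-daily values alone.

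What remains is that the number of tests is under unblinded control and is nowhere reported by arm.

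**Conclusion.** The gap is real and conditional. If sampling differs by arm, Table E4's extreme-value rows, highest creatinine and stage II AKI can differ with no fluid effect. At 7,500 per arm, 10% more draws gives P<0.05 in about 8-35% of trials and 20% more in about 18-85%; 5% more barely matters. These figures, computed for the threshold rows, assume equal arms, extra draws unrelated to the value, a simple two-proportion test that ignores ICU clustering, and variances that the sponsor can replace with its own.

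The documents do not support concluding that sampling did differ. They also do not support carrying the concern over to MAKE30, whose creatinine component uses the final inpatient value rather than an extreme. The point bears on what the abnormal-laboratory and any-value creatinine results can be taken to show, and the remedy is cheap enough that it should be adopted.

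**What to change.** - Keep Table E4 on all values. Beside it, add a version using one value per patient-day, the one closest to 0800.
- Report, by arm and for each analyte including creatinine, draws per patient-day and the number of days with any draw. Show the creatinine counts with highest creatinine and stage II AKI.
- State in the SAP that an abnormal-value difference will be read as a fluid effect only if it also appears in the once-daily version.

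Cost: analysis code and SAP wording. All serum values are already collected (2017 protocol, 8.4.1 and 8.4.2), and the baseline creatinine rule already relies on their timing. Downside: once-daily values miss transient extremes, which the all-values version still shows. They also do not correct a difference in the number of days sampled, which is why the draw and day counts are an essential part of the change.
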